D5. Data Analysis. Data will be managed using REDCap (Research Electronic Data Capture; which is HIPAA compliant).⁶⁸ Primary analysis will be group differences in TUG times (primary outcome) at the 12-week time point. As a pilot feasibility study, data will only be analyzed for participants with sufficient intervention exposure, defined as six weeks. For participants who withdraw at or beyond six weeks of intervention, an early termination test will be performed and carried forward as the end-point. Participants who withdraw before completing six weeks will be lost to follow-up and no imputation will be performed for missing data. Attempts will be made to test all participants at 24-weeks. However, missing 24-week data will not be imputed from the 12 week measurement, as this would bias the effect following the primary end-point (i.e., it is expected that both groups would have worse 24- compared to 12-week outcomes). Group differences will be based on a linear model with TUG as the outcome and explanatory variables being primary medical diagnosis (PAD, DM, or both), rehabilitation site, treatment group, and baseline TUG. Group differences will be determined by this single test to protect against Type I error (α level: 0.05).

Secondary analyses will include differences at 12-weeks in the other outcomes (2MW, 5mW, PEQ-MS 12/5, Houghton Scale, PSFS, Activity level, number of healthcare provider visits, and number of hospital encounters) using the same method as for the primary outcome. A mixed-effects model with time as a fixed covariate across baseline, 12-, and 24-weeks will be used to evaluate long-term outcomes (24-week) and make inferences regarding the effectiveness of the intervention up to 12-weeks after intervention is complete. As with the other analyses, evaluation of the time trajectory will be conditioned on stratification variables and baseline values of the outcome measure. Also the mixed-effects model will not include data from subjects who drop prior to 6 weeks.

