Collaborative-Care Rehabilitation to Improve Functional Outcomes after Dysvascular Amputation

Statistical Analysis Plan
Version Date: 01.05.2014

Between-group differences in all outcomes at 12- and 24-week tests will be evaluated using maximum likelihood estimation in a multivariate repeated measures model. The maximum likelihood method uses all available data and provides unbiased estimates under the assumption that missing data are missing at random. The model for each outcome will be controlled for baseline value of the outcome, rehabilitation clinic site (VA/non-VA), diagnosis of DM, and diagnosis of PAD. Estimated group means and within-group mean changes over time for each outcome will be reported with 95% confidence intervals. This early phase study is powered for one endpoint; multiple secondary endpoints are reported to guide further research without adjustment for multiplicity.

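### The 24-week mixed model in Protocol D5 uses baseline as both response and covariate without naming covariance or contrast, and D5 and the SAP specify the 12-week TUG analysis differently

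*Protocol*

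**What the plan says.** **24-week model, Protocol D5.** The model is introduced with "A mixed-effects model with time as a fixed covariate across baseline, 12-, and 24-weeks will be used to evaluate long-term outcomes", so baseline is one of three modelled occasions. D5 then adds "As with the other analyses, evaluation of the time trajectory will be conditioned on stratification variables and baseline values of the outcome measure", so the same value is also a covariate. On exclusions it says "Also the mixed-effects model will not include data from subjects who drop prior to 6 weeks", although it also says "Attempts will be made to test all participants at 24-weeks". It does not give the random effects or covariance, whether time is categorical, whether there is a group-by-time term, or which contrast answers the 24-week question.

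**12-week TUG, Protocol D5.** The primary analysis is one linear model, with "explanatory variables being primary medical diagnosis (PAD, DM, or both), rehabilitation site, treatment group, and baseline TUG". It is limited to participants with at least six weeks of intervention. For those who withdraw at or after six weeks, an early-termination test is carried forward as the end-point.

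**SAP.** One model covers everything: "Between-group differences in all outcomes at 12- and 24-week tests will be evaluated using maximum likelihood estimation in a multivariate repeated measures model". It is "controlled for baseline value of the outcome, rehabilitation clinic site (VA/non-VA), diagnosis of DM, and diagnosis of PAD". On missing data, "The maximum likelihood method uses all available data", under missing at random. The SAP mentions neither the six-week rule nor carry-forward.

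The two documents carry the same date if the SAP's 01.05.2014 is in US order. Neither states precedence.

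**The concern.** When baseline is a response and also a covariate, the covariate equals the response on the baseline row. A single baseline slope fitted across all three occasions is pulled toward 1 by that row, and the baseline residuals are artificially small. If the model pools residual variance over occasions, the week-24 standard error is too small.

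The claims that effects persist at 24 weeks in H1.1, H1.2 and H2 rest on this model. Analysts who follow D5 faithfully could report different 24-week intervals, and one ordinary choice gives intervals that are too narrow.

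The second issue reaches the primary endpoint. D5 protects type I error by relying on a single test of 12-week TUG, yet the SAP's model for all outcomes also covers 12-week TUG, with different rules. With about 34 participants expected at week 12, the choice can move the primary interval.

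**Working it through.** **Inputs.** D6 gives 17 per group at week 12, an effect of 6.0 s and an SD of 6.0. These reproduce: a two-sample t-test at effect size 1.0 has power 0.807 with 17 per group and 0.781 with 16. D5 gives alpha 0.05; two-sided is assumed. The documents give no correlation between visits, so equal correlations r = 0.3 / 0.5 / 0.7 are assumed. Error rates do not depend on the common SD, so variances below are in units of SD squared.

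**Random intercept, categorical time, week-24 group contrast.**

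- The slope on baseline is 1 in the baseline row and r in each follow-up row, so the pooled slope is b = (1 + 2r)/3.
- True residual variance at week 24 is 1 + b² − 2br.
- The model uses the average over the three rows, [(1 − b)² + 2(1 + b² − 2br)]/3, which equals (4/9)(1 − r)(2 + r).

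| r | b | baseline-row variance | true week-24 variance | model variance | SE ratio | large-sample error |
|---|---|---|---|---|---|---|
| 0.3 | 0.533 | 0.218 | 0.964 | 0.716 | 0.861 | 9.1% |
| 0.5 | 0.667 | 0.111 | 0.778 | 0.556 | 0.845 | 9.8% |
| 0.7 | 0.800 | 0.040 | 0.520 | 0.360 | 0.832 | 10.3% |

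Simulation with 17 per arm, no effect, REML and Satterthwaite t (20,000 trials per setting) gives 9.1% / 9.9% / 10.3%. Week-24 ANCOVA, checked in a separate run of 15,000 trials, gives 4.8% / 5.0% / 5.1%. The large-sample limit agrees, so more participants would not cure it. If correlations decay with time (adjacent 0.3 / 0.5 / 0.7, squared for baseline to week 24), the error rises to 10.1% / 12.0% / 13.9%.

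**Group-by-time contrast, same model.** The baseline covariate is constant within a participant and cancels from the change. The contrast compares mean change, with variance proportional to 2(1 − r), which the model estimates correctly under equal correlations. Simulated error is 5.4% / 5.3% / 5.0%. ANCOVA has 1 − r², so the variance ratio is 2/(1 + r) = 1.54 / 1.33 / 1.18. Under decaying correlation the error is 7.5% / 8.5% / 9.5%, but that comes from the constant-correlation assumption and not from the double use.

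**Unstructured covariance, week-24 contrast.** The baseline row can be fitted exactly with slope 1 and residual variance near zero, so the contrast again becomes a change-score test. A small check (400 null trials, r = 0.5) gave slope 1.000 and rejection 4.3%, with Monte Carlo error of about 2 points. Software would probably flag a singular fit.

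**12-week TUG, D5 against SAP.**

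| | Protocol D5 | SAP |
|---|---|---|
| Model | single linear model | maximum likelihood repeated measures |
| Analysis set | at least six weeks of exposure | all available data |
| Withdrawal at or after six weeks | early-termination test carried forward | missing at random, no carry-forward |
| Diagnosis | three categories | separate DM and PAD terms |
| Site | rehabilitation site | VA/non-VA |

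D5's linear model simulates at 5.1% / 4.9% / 5.1%. Maximum likelihood with a z reference gives 7.1% / 6.8% / 7.1%, or 8.2% / 8.0% / 8.0% with three further binary covariates. The SAP names no reference distribution. With t on 31 df, the ML-to-REML variance ratio is about 31/34, so the critical value 2.040 shrinks to 2.040 × √(31/34) = 1.947, an error of about 6.1%. With 28 df and ratio 28/34 the same arithmetic gives about 7.4%.

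**The case against.** The strongest reply is that the SAP already removes the double use. It models the 12- and 24-week tests and adjusts for baseline, which reads most naturally as baseline used once. That is right, and following the SAP would cure the 24-week model. But D5 does not say so and neither document gives precedence. Adopting the SAP also changes the primary 12-week analysis that D5 sets out.

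A reader might infer that D5's 24-week test has roughly double the stated error rate. The documents do not support that. The 9-10% needs a random intercept and a week-24 level contrast, and D5 states neither. Its reference to a time trajectory fits a group-by-time contrast at least as well, and that contrast is near nominal under equal correlations. The inflation comes from pooling variance across occasions and does not follow from the double use under every covariance.

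A reader might also infer that the SAP's model runs at 7-8% for 12-week TUG. That assumes a z reference; with t it is about 6-7%.

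On stakes, D5 claims type I protection only for its single primary test, and the SAP presents secondary endpoints as guidance for further research. This limits the weight of the 24-week issue but does not bear on the conflict over 12-week TUG. Finally, the matching dates depend on US order; read day-first, the SAP would be the later document, still without a statement that it supersedes D5.

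**Conclusion.** The point holds in two parts.

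First, D5's 24-week model is ill-specified. Under equal correlations, the ways of fitting it examined here with baseline in both roles give either intervals that are too narrow (SE about 14-17% too small, error about 9-10%) or a change-score test that gives up the precision of baseline adjustment (variance 1.18-1.54 times ANCOVA). These figures assume 17 per arm, complete data, equal variances and equal correlations of 0.3-0.7. The analysis is secondary, and it would be wrong to conclude that D5's primary 12-week linear model is compromised by the double use.

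Second, 12-week TUG has two specifications that differ in model, analysis set, treatment of early-termination values and covariates, with no rule for choosing between them. This part needs no assumption about correlation; it follows from setting the two texts side by side. The meaning of stratification variables in D5 is also open. It may refer to the diagnosis and site terms of the primary model, or to sex, the only factor by which randomization is stated to be stratified and one that neither covariate list contains.

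Both parts should be corrected before analysis.

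**What to change.** Replace the mixed-model sentences in D5 with:

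- responses at weeks 12 and 24 only, with baseline as a covariate;
- group, categorical time and group-by-time, with unstructured covariance;
- the week-24 group difference as the named contrast;
- REML with a small-sample t reference, such as Kenward-Roger.

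An acceptable alternative uses baseline as a response only, with equal baseline means across arms and no baseline covariate.

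In both documents, state:

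- which model is primary for 12-week TUG;
- one analysis set, including whether someone who drops before six weeks but is tested later counts;
- one rule for the early-termination value;
- one covariate list, saying what stratification variables means and whether sex is included.

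The cost is wording, with no added data. The 24-week t-intervals would be about 16% / 19% / 22% wider than the random-intercept reading would print (r = 0.3 / 0.5 / 0.7), but correctly calibrated. At r = 0.5, for example, the SE ratio is √(0.75/0.556) = 1.16, and the smaller degrees of freedom account for the rest. Against the change-score readings the new intervals are narrower: change-score intervals are 19% / 12% / 5% wider.

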Collaborative-Care Rehabilitation to Improve Functional Outcomes after Dysvascular Amputation

Protocol Version: January 5, 2014

COMIRB Protocol

COLORADO MULTIPLE INSTITUTIONAL REVIEW BOARD
[name] [contact] [contact]

Title: Collaborative-Care Rehabilitation to Improve Functional Outcomes after Dysvascular Amputation

Principal Investigator: [name], PT, Ph.D.
V1.3

SYNOPSIS

Objectives

The objective of this study is to determine the efficacy of a collaborative-care, home-based rehabilitation program for improving functional outcomes following dysvascular transtibial amputation. The primary aim is to determine if the rehabilitation program improves performance-based and participant-report measures of physical function, compared to standard of care, for participants with dysvascular transtibial amputation. The secondary aim is to determine if the rehabilitation program improves daily physical activity, compared to standard of care, for participants with dysvascular transtibial amputation. Two exploratory aims are: 1) determine the efficacy of the intervention for promoting health self-management, measured as participant-reported self-efficacy for managing chronic disease, motivation for exercise, and health-care resource use and 2) identify factors at initial testing that are predictive of physical activity level and disability 24 weeks after intervention.

Design and Outcomes

This will be a randomized, controlled clinical trial on the effects of 12 weeks of collaborative-care, home-based rehabilitation on physical function outcomes. Outcome variables include:

1. Performance-Based Physical Function Measures:
 - a. Timed Up-and-Go (TUG)¹
 - b. Two-Minute Walk (2MW)²
 - c. Five-meter Walk (5mW)³
2. Self-Report Physical Function Measures:
 - a. Prosthesis Evaluation Questionnaire – Mobility Section (PEQ-MS)⁴
 - b. Houghton Scale⁵
 - c. Patient-Specific Functional Scale (PSFS)⁶
3. Activity Measurement:
 - a. Physical activity monitors (Actigraph) worn for 1 week following each test session (baseline, 12-week, 24-week). These monitors are valid tools for measuring relative level of activity (e.g., sedentary, light, moderate, vigorous) for various patient populations⁷⁻⁹ and are valid and reliable spatiotemporal gait measures for patients with lower limb amputation.^{10,11}
4. Self-Efficacy and Motivation:
 - a. Self-Efficacy in Managing Chronic Disease (SEMCD) questionnaire^{12,13}

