 - b. Intrinsic Motivation Inventory (IMI) Interest and Enjoyment Subscales¹⁴
 - c. Participant compliance with exercise will be tracked as number of exercise sessions missed/possible sessions.
5. Healthcare Use:

- a. Number of healthcare provider visits scheduled and attended; from electronic medical record.
- b. Number of hospital contacts (emergency department visits and hospital admissions); from electronic medical record.

Interventions and Duration

Forty-four participants will be randomly assigned to two groups: 1) experimental (EXP) or 2) control (CTL). The entire intervention period is 12 weeks, with the primary end point at 12 weeks. At 24 weeks after initiation of intervention, each group will be asked to return for a follow-up test session.

Evaluations will take place using the following schedule:

Baseline, 12 and 24 weeks: Physical Performance Tests, Self-Report Physical Function Measures, Activity Measurement, Self-Efficacy questionnaire, Motivation questionnaire, Health Status questionnaire, and healthcare use assessment.

Baseline only: At Baseline testing, participants will also complete the following tests/measures/forms: 1) Folstein Mini-Mental State Examination,¹⁵ 2) Geriatric Depression Scale SF,^{16,17} 3) Chakrabarty scoring of residual-limb quality,¹⁸ 4) Residual limb length, 5) lower extremity sensory testing, 6) pre-amputation ambulatory status report, 7) type of prosthesis (socket, suspension, and foot), and 8) demographic information. Hemoglobin A1c measurements (for DM) and confirmation of PAD will be extracted from the participant medical records.

Continuously: Falls, Adverse Events (AEs), and Serious Adverse Events (SAEs) will be recorded and reported as needed.

Sample Size and Population

The target sample is 44 persons with recent transtibial amputation, resulting from PAD or DM complications.

Participants will be recruited from the University of Colorado Hospital and Denver Health.

Title: Collaborative-care rehabilitation to improve functional outcomes after dysvascular amputation

A. Abstract & Specific Aims

The primary objective of this project is to determine the efficacy of a collaborative-care, home-based exercise program for improving physical function, activity level, and health self-management within the first year following dysvascular transtibial amputation.

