 - (1) H3: The rehabilitation program group will tend to have greater positive change in ratings on the Self-Efficacy in Managing Chronic Disease (SEMCD) questionnaire and Intrinsic Motivation Inventory (IMI) Interest and Enjoyment Subscales, compared to the standard of care group at 12 and 24 weeks following initiation of intervention.
 - (2) H4: The rehabilitation program group will tend to have higher numbers of attended healthcare provider appointments and lower numbers of hospital contacts at 12 weeks and 24 weeks, compared to the standard of care group.

2. Exploratory Aim 2 (EA2) and Hypothesis (H4) are:

- a) EA2: Identify factors predictive of physical activity level and disability measured by activity monitors and self-reported disability (World Health Organization Disability Assessment Schedule 2.0), respectively.
- b) H5: Significant predictors of physical activity and disability will be identified from the categories of demographic/anthropometric, activity/mobility, health behaviors, physical health, amputated-limb health, contralateral-limb health, cognitive/affective health, and healthcare use factors for participants at 24 weeks following intervention, regardless of group assignment.

B. Background and Significance

B1. Significance. Limitations in physical function are common following dysvascular major lower limb amputation.^{28,29,31} This is a significant issue considering that dysvascular amputation is becoming increasingly more common in the United States. Dysvascular amputation is operationally defined as amputation resulting from severe PAD with critical limb ischemia or severe DM with dense distal sensory and motor neuropathy leading to a non-healing wound (or a combination of these two related, but separate pathophysiologies). The projection of 2.3 million people living with amputation in the United States by the year 2050 represents an increase of nearly 100% from current values.¹⁹ As a result, dysvascular amputation has become a major healthcare issue in the U.S, including an economic problem.³²

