D2. Inclusion/Exclusion Criteria. Inclusion criteria: 1) DM and/or PAD, 2) unilateral transtibial amputation < 6 months prior to baseline testing, 3) household ambulation using definitive prosthesis prior to baseline testing, 4) participation in physical rehabilitation at time of baseline testing and 5) live within 45 minutes of a participating clinic.

Exclusion criteria: 1) require wheelchair for mobility (use prosthesis only for transfers), 2) ankle-level or above amputation on contralateral limb, 3) traumatic or cancer-related amputation, 4) uncontrolled heart condition, 5) acute systemic infection, 6) pregnancy, 7) decisionally challenged, and 8) prisoners.

Confounding variables will be tracked to allow better delineation of the “dysvascular amputation” population in future studies including: medications, cognitive function (Folstein Mini-Mental State Examination¹⁵), depression (Geriatric Depression Scale SF^{16,17}), residual limb quality (Chakrabarty scoring of residual-limb quality¹⁸), residual limb length, ankle-brachial index of the non-amputated limb, lower extremity sensory testing, pre-amputation ambulatory status (self-report), and type of prosthesis (socket, suspension, and foot). A Comorbidity Assessment tool¹⁶ will be used to document and account for comorbidities.

D3. Screening. Participants will be recruited at the rehabilitation site and screened with a phone call interview. After consent, participants will have an

based rehabilitation program are to: 1) improve physical impairments with targeted exercise, 2) increase physical activity through a home walking program and 3) optimize patient health self-management. The collaborative-care, home-based rehabilitation program was developed based on self-management programs for patients with chronic disease,^{45,46,57}

common physical impairments and functional limitations following dysvascular transtibial amputation,^{36,58-62} published standard of care guidelines based on professional opinion,^{34,63,64} and clinician input from the participating hospital systems (Table 3). Physical impairments and functional limitations will be individually identified at initial testing and interventions chosen with collaboration of participant and researcher. Participants will be contacted once/week via phone to discuss progress toward individual intervention goals. Barriers to achieving goals will be discussed and new goals created on a weekly basis during the phone or home visits.

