The exploratory aim of identifying predictors of physical activity and disability will be analyzed by regression analysis. First, variables will be grouped into demographic/anthropometric, activity/mobility, health behaviors, physical health, amputated-limb health, contralateral-limb health, and cognitive/affective health, and healthcare use factors. A hierarchical process will be used to screen variables within each group of factors to identify the best predictors within each group. Finally, the best predictor variables from each group will be entered into a regression model to determine models containing subsets of the variables that predict the outcome, based on R^2_{adj} . The most parsimonious model will be identified by comparing the 10 best models, using partial F-tests.

D6. Sample Size Estimate. Sample size was estimated using TUG means and variances at discharge from the ongoing pilot study. In addition, literature was used to estimate long-term (> 3 months post-amputation) TUG scores for the population.^{60-62,69,70} Using 12.4 (3.9) seconds mean (SD) TUG time at rehabilitation discharge from the first 14 participants in the pilot study and 19.3 seconds as the average of TUG time reported for patients several months to years after amputation, a group difference of approximately 6.0 seconds was expected in TUG times at the 12-week time-point (primary end-point). With this group difference and an estimated SD of 6.0 (effect size = 1.0), 17 participants per group would provide 80% power to identify differences. The assumption is the EXP group will maintain or improve TUG times after the 12-week intervention and the CTL group will decline toward levels reported in the literature. A 3.4 second change in TUG represents a minimal detectable change for patients with lower limb amputation.⁶⁹

The goal is to enroll 44 participants and graduate 17 participants per group (n=34) at the 12-week test point. Based on data from the four participating hospitals, 150 patients will complete rehabilitation and achieve functional ambulation following dysvascular transtibial amputation

over the next 3 years. Based on the pilot study (Section C2), 60% of these patients are expected to meet inclusion/exclusion criteria (n = 90) and 50% of those will agree to participate (n = 45). A 20% loss to follow-up at 12 weeks (n=34) is estimated, which is twice the observed rates of studies with 12-week end-points that the PI has been involved with for other patient populations.

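### Exploratory Aim 2 chooses its predictors and judges them in the same small sample with no correction for the search, and H5 invites reading the result as significance

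*Protocol*

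**What the plan says.** The Synopsis (Objectives) sets the aim: "identify factors at initial testing that are predictive of physical activity level and disability 24 weeks after intervention". There are two outcomes, monitor-measured activity and self-reported disability (WHODAS 2.0). Both arms are pooled.

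The protocol's D5 gives the method in three steps:

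1. Candidates are sorted into eight factor groups, and "A hierarchical process will be used to screen variables within each group of factors to identify the best predictors within each group".
2. The survivors enter a regression, and subsets are ranked by adjusted R².
3. "The most parsimonious model will be identified by comparing the 10 best models, using partial F-tests".

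The hypothesis attached to this (Exploratory Aims, H5) reads: "Significant predictors of physical activity and disability will be identified from the categories of demographic/anthropometric", followed by the other seven categories.

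On numbers, D6 says: "The goal is to enroll 44 participants and graduate 17 participants per group (n=34) at the 12-week test point". No 24-week number is given, and D5 rules out filling missing 24-week data from the 12-week measurement. The candidates in each group, the screening rule and the level of the partial F-tests are not stated. No split sample, cross-validation, bootstrap or shrinkage appears in either document. The SAP deals with between-group differences only and does not mention this regression.

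**The concern.** The same participants are used to screen variables, rank models, choose one and, presumably, describe how good it is. The t-tests and R² of a model chosen this way are computed as if the model had been fixed beforehand. They therefore ignore the search and err in one direction: p-values too small, R² too large. Adjusted R² charges for the terms in a given model, not for the candidates and subsets tried on the way to it.

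The plan does not say outright that p-values or R² of the final model will be reported. H5 makes it likely that they will be, and that they will be read as evidence. Noise variables could then be presented as significant predictors of activity and disability, with an R² the model would not reach in new people. Section A says the results are meant to inform future research, which is where the error would be carried. The primary TUG analysis and the secondary group comparisons are not touched.

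**Working it through.** **Inputs.** Eight factor groups (D5); 44 enrolled and 34 at 12 weeks (D6). Because the 24-week number is not given, n = 28, 34 and 44 were used; 28 is an assumption for further loss. The candidate number is also an assumption: 1 per group, 3 per group, or the measures the protocol names. My allocation of the last comes to 2 + 10 + 2 + 5 + 3 + 2 + 2 + 2 = 28:

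- demographic/anthropometric 2 (assumed, since the content is not itemised)
- activity/mobility 10: TUG, 2MW, 5mW, single-limb stance, PEQ-MS, Houghton, PSFS, WHODAS 2.0, activity monitor, pre-amputation ambulation
- health behaviors 2: SEMCD, IMI
- physical health 5: comorbidity tool, health status, DM/PAD diagnosis, medications, and HbA1c (Synopsis: "Hemoglobin A1c measurements (for DM) and confirmation of PAD will be extracted from the participant medical records")
- amputated limb 3: Chakrabarty score, limb length, prosthesis type
- contralateral limb 2: ankle-brachial index, sensory testing
- cognitive/affective 2: Mini-Mental State, depression scale
- healthcare use 2: provider visits, hospital contacts

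**The plan's own figure.** The documents give no figure for this aim. The 34 comes from the TUG sample size, which reproduces: for difference 6.0, SD 6.0 and two-sided 0.05, a t-test needs 16.7, so 17 per group (power 80.7%). With 20% loss, 34 / 0.80 = 42.5, so 43, against 44 planned.

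**A simple bound.** For m independent null candidates each tested at 0.05, P(at least one p < 0.05) = 1 − 0.95^m. This is 34% for m = 8, 71% for m = 24 and 76% for m = 28.

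**Simulating the three steps.** Normal variables; groups independent of each other; the best candidate per group taken by absolute correlation; all 2⁸ − 1 = 255 subsets of the eight winners ranked by adjusted R². The final model is the smallest of the top 10 that is nested in the best one and not rejected by a partial F-test at 0.05. The one-winner rule, the F-test level and the independence are assumptions. Rates are per outcome.

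*No real predictor* (6,000 data sets per setting, ±1.3 points; the correlated rows 2,000):

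| Candidates | Final model has a p < 0.05 variable, n = 28 / 34 / 44 | Mean apparent R² (truth 0) |
|---|---|---|
| 1 per group | 46 / 43 / 41% | 0.21 / 0.17 / 0.13 |
| 3 per group | 85 / 84 / 81% | 0.40 / 0.34 / 0.27 |
| 28 measures | 86 / 85 / 84% | 0.41 / 0.34 / 0.27 |
| 28, within-group correlation 0.5 | 81 / 80 / 79% | – |
| 28, within-group correlation 0.7 | 77 / 75 / 72% | – |

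*Adjusted R²*, the plan's ranking measure, is 1 − (1 − R²)(n − 1)/(n − p − 1). In smaller separate runs (600 data sets per setting) with no signal at n = 34 it averaged 0.12 with 1 per group and 0.26 with 3 per group, while R² in new participants was −0.21 and −0.40. With the 28 measures adjusted R² was 0.27.

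*A different screening rule.* Forward selection within each group at entry p < 0.05, 0.10 or 0.20, keeping several variables or none (500 data sets each, ±4 points), gave for 1 per group, 3 per group and 28 measures: 31–38%, 69–82% and 76–87% at n = 34; 33–39%, 70–78% and 78–86% at n = 44. Apparent R² over both n was 0.05–0.12, 0.12–0.29 and 0.15–0.34.

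*One real predictor*, in the activity/mobility group (28 measures, within-group correlation 0.5, one winner per group, 2,000 data sets). With slope b in residual SDs, true R² = b²/(1 + b²): b = 0.5, 0.75 and 1.22 give 0.20, 0.36 and 0.60. Noise means any variable outside that group.

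| n | True R² | Apparent R² | R² in new people | Final model also flags noise at p < 0.05 |
|---|---|---|---|---|
| 34 | 0.20 / 0.36 / 0.60 | 0.42 / 0.51 / 0.68 | −0.15 / 0.11 / 0.48 | 64 / 60 / 54% |
| 44 | 0.20 / 0.36 / 0.60 | 0.36 / 0.47 / 0.66 | −0.05 / 0.18 / 0.51 | 60 / 59 / 52% |

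The gap narrows as the true signal grows. Smaller runs gave 50–51% noise flags at true R² 0.60 and n = 34, so about half is the fair reading there.

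**The case against.** The aim is labelled exploratory, the trial calls itself a pilot feasibility study, no alpha is attached to this aim, and the plan does not promise to report post-selection p-values. The harm depends on how someone later reads the output. That stands, and it is why the point is minor. But the caveat about low power and looking for trends is attached to Exploratory Aim 1 only, and the SAP's remark about guiding further research concerns secondary endpoints. This aim has no such caveat and is worded in terms of significance.

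The complete null is also the least plausible case, since baseline activity and baseline WHODAS are natural candidates for their own 24-week values. This is fair: with a real predictor the overstatement is smaller, though the final model still flags a noise variable in half or more of data sets. The real-predictor results use only the one-winner rule, whereas D5 speaks of predictors in the plural; the rule that keeps several was run only without signal.

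The count of 28 is a reading, not a statement in the protocol. D5 names healthcare counts among the 12-week outcomes, although the Synopsis also schedules healthcare use at baseline. Nothing says outright that baseline WHODAS is a candidate. With no signal and n = 34 to 44 the flag rate runs from 31% to 87% across the settings, so the documents do not fix the size.

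Adjusted R² is lower than the unadjusted figure, and it is the measure the plan ranks on. It is still 0.12 to 0.27 at n = 34 when the truth is 0, so the bias remains.

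**Conclusion.** The concern holds, as a minor one. Selection and assessment use the same small sample, nothing corrects for this, and the wording of H5 encourages a reading the analysis cannot support. The direction of the bias is the same in every setting tried. Even with one candidate per group, where the first screen does nothing, about four in ten no-signal final models show a nominally significant predictor under the one-winner rule (n = 34 and 44). The size rests on assumed candidate numbers, screening rule, F-test level, correlation and 24-week n, and should be read as a range.

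**What to change.** In D5, fix the candidate list for each group and the within-group screening rule before the 24-week data are examined, so that the process can be repeated by program. Then add:

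> The whole selection process, including the within-group screening, will be repeated in bootstrap resamples; the optimism-corrected R² and each variable's selection frequency will be reported. P-values of the selected model will not be presented as evidence of significance.

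In H5, replace significant predictors by candidate predictors. The adjusted R² ranking and the partial F-tests can stay. If a test is wanted, permute the outcome and rerun the whole procedure.

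A check of the bootstrap (28 measures, within-group correlation 0.5; 150 data sets, 80 resamples each, standard error about 0.015) gave:

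| n | True R² | Apparent | Corrected | New people |
|---|---|---|---|---|
| 34 | 0 | 0.30 | −0.27 | −0.39 |
| 34 | 0.36 | 0.49 | 0.10 | 0.10 |
| 34 | 0.60 | 0.68 | 0.46 | 0.48 |
| 44 | 0 | 0.26 | −0.20 | −0.35 |
| 44 | 0.36 | 0.48 | 0.20 | 0.17 |
| 44 | 0.60 | 0.65 | 0.50 | 0.52 |

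With no signal the correction is incomplete, but at n = 34 the corrected value is 0 or below in 91% of data sets. Selection frequency at n = 34 was 64% and 93% for the real predictor (true R² 0.36 and 0.60) and 11–12% for the others. The permutation test at 0.05 and n = 34 rejected in 4% of data sets with no signal, 52% at true R² 0.36 and 90% at 0.60 (99 permutations; 400, 120 and 60 data sets).

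The cost is a few sentences and some programming, with no new data. The price in reporting is a lower R² and no post-selection p-values offered as evidence for single predictors.
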